School of Experimental Psychology [name] United Kingdom

[name] t. [name] f. [contact] www.bristol.ac.uk

STUDY PROTOCOL

Effects of alcohol consumption on emotion recognition

[name], [name], [name], [name]

Background Information

Alcohol is often consumed in social settings whilst in the company of others. Recent research has begun to examine the effects of acute alcohol consumption on the processing of socially relevant information such as facial expressions, as it may play a role in the changes in social interaction associated with alcohol consumption (e.g., increased aggression) (Attwood & Munafo, 2014; Hoaken, Giancola, & Pihl, 1998; White, 1997; Yudko, Blanchard, Henrie, & Blanchard, 1997). Recent research has indicated that acute alcohol consumption decreases sensitivity to recognising sad facial expressions (Craig, Attwood, Benton, Penton-Voak, & Munafo, 2009) and increases the likelihood of perceiving anger in ambiguous facial morphs (Attwood, Ataya, Benton, Penton-Voak, & Munafo, 2009). To date this research is limited, with studies only examining the effects of alcohol on a small number of emotions.

We recently explored the effect of acute alcohol consumption (0.4 g/kg) on emotional face processing using a task that presents all six primary emotional expressions (i.e., anger, sadness, happiness, surprise, disgust and fear). We found no difference between alcohol and placebo in accuracy of emotional identification, but there were greater false alarms for anger after alcohol compared to placebo (i.e., individuals were more likely to erroneously label a non-angry face as angry). In addition, alcohol consumption was associated with fewer false alarms for happiness compared to placebo. The current study will attempt to replicate these findings using the same six alternative forced-choice task (6AFC). In addition, this study will include a two alternative forced choice task (2AFC) presenting angry and happy facial morphs, to investigate whether there is a bias towards the identification of anger after acute alcohol consumption.

Study Objective and Hypotheses

To replicate preliminary work on the effects of acute alcohol consumption on emotional face processing.

H1: Acute alcohol consumption will result in more false alarms for anger compared to placebo.

H2: Acute alcohol consumption will result in fewer false alarms for happiness compared to placebo.

Study Design

This is a double-blind placebo-controlled study, which comprises one between-subjects factor of drink (0.4 g/kg alcohol, placebo). For the 6AFC task, there will be an additional within-subjects factor of emotion (happy, sad, angry, disgust, surprise, fear). The primary dependent variables will be accuracy and false alarms in the 6AFC task, and threshold in the 2AFC task. As 6AFC data are the primary outcome, the 6AFC task will be completed first for all participants. To investigate the subjective effects of alcohol, additional measures of intoxication and mood will be taken (see materials section) before and after drink consumption, and an additional factor of time (pre-inhalation, post-inhalation) will be included in the relevant analyses.

Study Site

School of Experimental Psychology, [name], University of Bristol, United Kingdom.

Participants and Recruitment

Male and female weekly alcohol drinkers (n = 192; 50% male) will be recruited from the staff and students at the University of Bristol, and the general population. Participants will attend one session of approximately 60 minutes. Participants will be recruited by existing email lists and poster and flyer advertisements, and by word of mouth. They will be asked to contact the researcher for further details of the study if they are interested in taking part. Those who meet the study inclusion criteria will be sent the information sheet, and asked to contact the researcher again if they would like to sign up for the study or if they require further information. Participants will be required to not drink alcohol 24 hours prior to the study session. On completion of the study, participants will be reimbursed £5.

Inclusion criteria

- Aged between 18-40 years
- Weekly alcohol drinkers (between 5-35 and 10-50 units*/week if female and male respectively)
- English as first language or equivalent level of fluency

^{*} One unit equals one 25ml single measure of spirit (ABV 40%), or a third of a pint of beer (ABV 5-6%) or half a standard (175ml) glass of red wine (ABV 12%).

Exclusion criteria

- Alcohol consumption less than 24 hours prior to the study
- Weight less than 50 kg if female or 60 kg if male
- Strong familial history of alcoholism defined as one or more immediate relative (parent, sibling) or more than one other relative (e.g., cousin, grandparent)
- History of psychiatric disorder (including drug addiction)
- Uncorrected visual impairment
- Uncorrected auditory impairment
- Potential, in the opinion of the investigator, to be non-compliant with the study or unable to give informed consent

Sample size determination

Sample size was determined from an effect size obtained in the previous study investigating the effects of acute alcohol consumption on emotional processing. This study indicated an effect size of d = 0.41 for the comparison between alcohol (M = 4.8, SD = 4.2) and placebo (M = 3.2, SD = 3.6) on angry false alarms. Based on these data, we require a sample size of 190 in order to achieve 80% power at an alpha level of 5%. In order to maintain equal numbers of male and female participants in drink groups we will recruit 192 participants.

Randomisation

Participants will be randomly assigned to the alcohol or placebo group. Equal numbers of participants per group will be maintained and groups will be stratified by sex. In advance of the study, an experimental collaborator will prepare a numeric randomisation code using random number assignment software.

Measures

Computerised tasks: The images used in both tasks are composite (i.e., prototypical) images created from photographs of 12 young male adults photographed under controlled conditions. Each trial in both tasks begins with a centrally-displayed fixation cross. A 350×457 pixel face stimulus is then presented for 150 ms, followed by a noise mask for 250 ms in order to prevent after-image effects. Tasks are run using E-Prime 2.0 Pro software, on a standard computer with a QWERTY keyboard.

In the six alternative forced choice task (6AFC), six 15-image morph sequences have been created, one for each emotion (happy, sad, angry, disgusted, fearful, surprised). These run along a linear continuum from a neutral (i.e., emotionally ambiguous) prototype to the full emotional intensity. On each trial, participants are required to identify the emotion represented in the face as quickly and as accurately as possible, by using the mouse to click on the most appropriate descriptor from an array of descriptors displayed on-screen (fearful, angry, happy, sad, disgusted and surprised). The descriptor array appears on-screen for 10,000 ms, or until the participant responds. Each image is presented once, giving 90 trials in total.

In the two alternative forced choice task (2AFC), one 15-image morph sequence has been created, which runs from one full emotional exemplar to another (i.e., unambiguously happy to unambiguously angry). The full exemplar images are used as endpoints to create a linear morph sequence of emotionally ambiguous images that change incrementally from happy to angry. On each trial, participants are required to identify whether the emotion in the face is happiness or anger, by pressing designated keys on the keyboard. Each image is presented three times, giving 45 trials in total.

Questionnaires: The questionnaire measures will include the Alcohol Urges Questionnaire (AUQ) (Bohn, Krahn, & Staehler, 1995), Positive and Negative Affect Schedule (PANAS) (Watson, Clark, & Tellegen, 1988), Biphasic Alcohol Effects Scale (BAES) (Martin, Earleywine, Musty, Perrine, & Swift, 1993) and Alcohol Use Disorders Identification Test (AUDIT) (Saunders, 1993).

Procedures

Participant screening and baseline assessments: On arrival, participants will be given the opportunity to read the information sheet again, and will provide written informed consent. The researcher will run through a short screening procedure to verify eligibility. Participants will be weighed and then complete questionnaire measures (AUDIT, PANAS, BAES, AUQ).

Participants will then be randomised to receive either an alcoholic or non-alcoholic drink. The alcoholic drink will be 0.4 g/kg alcohol (vodka) with one part vodka and three parts tonic water. The placebo beverage will comprise an equal volume of tonic water. All drinks will be flavoured with lime cordial and chilled prior to serving and the rim of the glass will be sprayed with an alcohol mist. Drinks will be made by a research collaborator and therefore administered double blind. This collaborator will also produce an unblinding envelope that will be passed to the researcher with the drink, which will enable the researcher to inform the participant of their drink allocation at the end of the session. Participants will be given 10 minutes to consume all of their drink and a further 10 minutes to sit quietly to allow for absorption. After drink consumption, participants will complete the two computer tasks (see below) and then questionnaire-based measures of mood (PANAS), intoxication (BAES), and alcohol urges (AUQ). Finally, participants will be asked to give another breath alcohol reading before being debriefed and reimbursed.

Table 1. Timings of procedures of testing session

Time (minutes post arrival)	Task
0	Informed consent and screening
15	Questionnaire measures (4)
20	Drink administration
40	Task 1 – Emotional 6AFC
50	Task 2 – Emotional 2AFC
55	Questionnaire measures (3)
60	Debrief and depart

Statistical Plan

Analysis of the questionnaire scores will be conducted using mixed model ANOVAs with alcohol consumption (alcohol vs. placebo) as a between-subjects factors and time as a within subjects factor (before alcohol consumption, after alcohol consumption). Emotional task data from both tasks will also be analysed using ANOVAs with alcohol consumption as a between-subjects factor. The 6AFC task will have an additional within-subjects factor of emotion.

Ethical Considerations and Informed Consent

Ethics approval has been obtained from the Faculty of Science Research Ethics Committee at the University of Bristol. The study will be conducted according to the revised Declaration of Helsinki (2013) and good clinical practice guidelines. The investigator will explain the nature, purpose and risks of the study to the participant. The participant will receive the information sheet in advance of the study session. There will be no time restriction on how long participants take to respond, with the exception that participants who respond after all study places have been filled will not be offered a place on the study. Therefore, participants will be given sufficient time to read the information and consider any implications, and to raise any questions with the investigators prior to making a decision to participate. On arrival at the study session participants will be given the opportunity to read the information sheet again and ask the investigator any questions. Written consent will then be obtained. Participants will be informed that they are free to withdraw at any time.

Data Management

All aspects of the Data Protection Act will be adhered to. Consent forms will be retained by the School of Experimental Psychology. In the event that a participant revokes authorisation to collect or use personal health information, the investigator retains the ability to use all information collected prior to the revocation of participant authorisation.

Anonymised study data

The case report forms and data will be anonymised by a unique numeric identifier and stored in a locked office. All data requested on the CRF will be recorded. All missing data will be explained. If any entry errors are made, a single straight line will be drawn through the incorrect entry and the correct data entered above it; to correct such an error. All such changes will be initialled and dated. Once data from CRFs have been inputted into a data spreadsheet they will undergo a reliability check (20% check by independent researcher). After the data have been positively assessed, the CRFs will be destroyed in the School's confidential waste facility.

Original computer data files will be backed up immediately on a secured University of Bristol network drive. At the end of the electronic study data (including finalised data sheet) will be transferred to a designated University of Bristol Research Data Storage Facility. Study data will be kept for 5 years post study closure. At the appropriate time the data sheet will be locked and made open using the University of Bristol Data Repository.

Screening documents and participant contact details

Screening documents and participant names and contact details will be stored separately in a study master folder and kept confidential. These will be kept in the study master folder for one year post study completion, after which these documents will be destroyed. Failed screening documents will be shredded immediately using School's confidential waste facility.

Revoked data

If a participant decides that they do not want their data used after their participation they have the right to request that the data are withdrawn. They can request this up to one year post study completion or until the data are made open (whichever comes first). At this time links between participant identity and anonymised data set will be destroyed.

Safety

Half of the participants will be administered alcohol during the session. The dose will be 0.4 g/kg of body weight up to 90 kg. Participants weighing more than 90 kg will receive a dose based on 90 kg. This dosing will administer drinks ranging between around 2.5 to 4.5 units of alcohol (for weight ranges between 50-90 kg). We expect that at this dose, participants will feel some effects of alcohol but we do not expect high levels of intoxication. However, to ensure the safety of our participants, they will know in advance of the study that they may receive this dose of alcohol, and therefore will be able to make any necessary arrangements. They will also be unblinded at the end of the test session as to whether they received alcohol or not and the risks of alcohol will be reiterated. They will be advised that should stay behind until they feel the effects of alcohol have worn off and they shouldn't drive, operate heavy machinery or do anything that would be considered unsafe after drinking alcohol for the rest of the day. Participants who have received alcohol will be asked to read and sign a post-study safety form to confirm that they understand these risks. We have standard operating procedures in place for adverse effects of alcohol (i.e., nausea, intoxication) and have facilities for people to stay behind until they feel ready to leave. We will also offer a taxi home to all participants that have received alcohol.

Quality Control and Quality Assurance

The investigators will be responsible for data quality. After approximately 10% of data collection has been completed, the study will undergo an in-house quality assessment. During this monitoring process all CRFs and study documents will be assessed as well as the investigators laboratory management and participant engagement, and corrected where necessary.

Insurance

This study will be sponsored by the University of Bristol. The University has Clinical Research Insurance to cover the liability of the University to research participants. In the event that something goes wrong and a participant is harmed during the research

study there are no special compensation arrangements. If a participant is harmed and this is due to someone's negligence then they may have grounds for a legal action for compensation against Bristol University or other parties to the research, but they may have to pay their own legal costs.

Publication Policy

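### The exclusion list names neither pregnancy, breastfeeding, nor illness or medication that rules out alcohol, although half the sample is given 0.4 g/kg

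*Protocol*

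**What the plan says.** The protocol's inclusion criteria are age ("Aged between 18-40 years"), regular drinking ("Weekly alcohol drinkers (between 5-35 and 10-50 units*/week if female and male respectively") and fluency in English. Its exclusion criteria run to seven items. Two read "Weight less than 50 kg if female or 60 kg if male" and "History of psychiatric disorder (including drug addiction". The others are drinking in the previous 24 hours, a strong family history of alcoholism, uncorrected sight, uncorrected hearing, and a judgement item: "Potential, in the opinion of the investigator, to be non-compliant with the study or unable to give informed consent".

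Under Participants and Recruitment, "Those who meet the study inclusion criteria will be sent the information sheet". At the session, the Procedures section says "The researcher will run through a short screening procedure to verify eligibility". Weighing and baseline questionnaires follow, and then "Participants will then be randomised to receive either an alcoholic or non-alcoholic drink". The alcohol dose is 0.4 g/kg, calculated on no more than 90 kg, with 10 minutes to finish the drink.

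The Safety section provides for advance notice of the dose, advice and a signed form after the session, procedures for adverse effects, somewhere to stay, and a taxi. It describes no medical screening before the drink is given.

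**The concern.** The intervention is itself the hazard for some people, and the eligibility list is where a protocol says who must not receive it. This list excludes on psychiatric and family history but is silent on the physical conditions in which a rapid drink of alcohol may be unsafe. Since screening is described as a check of eligibility, a researcher who follows the written criteria has no listed reason to stop a participant who mentions a pregnancy or a new prescription. Recognising the problem and withdrawing is left to the participant, who does not learn the allocation until the end of the session.

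What is at stake is participant safety only. The omission does not bias the comparison, reduce power or affect the analysis.

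**Working it through.** **1. Coverage of the list.**

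| Exclusion item | Covers pregnancy or breastfeeding? | Covers physical illness or medication that rules out alcohol? |
|---|---|---|
| Alcohol in the previous 24 hours | No | No |
| Minimum weight | No | No |
| Family history of alcoholism | No | No |
| Psychiatric history, including drug addiction | No | No |
| Uncorrected sight | No | No |
| Uncorrected hearing | No | No |
| Investigator's opinion (non-compliance or inability to consent) | No | No |

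The result is 0 of 7. None of the three inclusion criteria covers these conditions either. A cooperative participant who is able to consent meets neither part of the judgement item, whatever she or he discloses.

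**2. Number given alcohol.** Inputs: 192 participants, 50% male (Participants and Recruitment); equal groups, stratified by sex (Randomisation).

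- Alcohol group: 192 / 2 = 96.
- Women in the alcohol group: 96 / 2 = about 48, all aged 18–40.

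**3. Dose.** Inputs: 0.4 g/kg with a 90 kg cap (Safety); minimum weight 50 kg for women and 60 kg for men (Exclusion criteria). The protocol's own figure of about 2.5 to 4.5 units is reproduced first, assuming 8 g of alcohol per unit:

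- 50 kg: 0.4 × 50 = 20 g; 20 / 8 = 2.5 units.
- 90 kg (cap): 0.4 × 90 = 36 g; 36 / 8 = 4.5 units.

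This matches. By sex, the range is 20–36 g for women and, since 0.4 × 60 = 24, 24–36 g for men.

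**4. Dose against habitual intake.** At the entry minimum for women, 5 units a week, one study drink is 2.5 / 5 = 50% to 4.5 / 5 = 90% of a week's intake. At the entry minimum for men, 10 units a week, it is (24 / 8) / 10 = 30% to 4.5 / 10 = 45%.

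**5. Where a check would fit.** Table 1 puts consent and screening at minute 0 and the drink at minute 20. Procedures puts randomisation after screening and the baseline questionnaires. An extra screening question would therefore be answered before allocation, and nobody would be removed after randomisation.

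**The case against.** There is a fair case that this is a minor matter of wording.

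- **Unseen documents.** The protocol refers to separate screening documents and an information sheet. Neither is available, and either may already ask about these conditions. If they do, the defect is a mismatch between form and protocol.
- **Other authority to stop.** The study commits to the Declaration of Helsinki and good clinical practice, has ethics approval, requires risks to be explained and allows withdrawal at any time. Nothing obliges a researcher to dose someone who discloses a contraindication.
- **Population.** Participants already drink every week, know beforehand that they may receive alcohol, and receive one drink that does not exceed the minimum weekly intake for entry.
- **Other safety measures.** The dose is capped, and there are procedures for adverse effects.
- **Size.** The 48 and the 96 are the people to whom a new item would apply, not the people at risk.

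Much of this stands. The safeguards lower the risk, the number affected is unknown, and there is no statistical consequence. The point is also confined to the listed criteria; it does not say that a researcher could find no other reason to stop. But none of these safeguards is an eligibility rule. Weekly drinking makes these conditions less likely without excluding a recent pregnancy, breastfeeding or a newly started medicine. Apart from the dose cap and advance notice, the Safety measures act after the drink. If the screening form does ask, the protocol should say the same, because the protocol defines who is eligible. Eligibility is also not something left to a statistical analysis plan.

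**Conclusion.** The concern holds. None of the seven exclusion items gives a ground to exclude a participant who discloses pregnancy, breastfeeding, or an illness or medication for which alcohol is contraindicated, and 96 people are to take 20–36 g of alcohol within 10 minutes. About 48 of them are women aged 18–40.

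These counts assume full recruitment, equal allocation and equal numbers of men and women in each group. They show how widely the added items would apply and are not an estimate of harm; the protocol gives no basis for one. Confidence is medium, because the screening form and information sheet could narrow the gap to one of wording. The change should be made for participant safety. The validity of the trial does not depend on it.

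**What to change.** Add two items to the exclusion criteria:

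- *pregnant, possibly pregnant or breastfeeding*;
- *current physical illness or medication for which alcohol is contraindicated*.

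Check both by self-report at the minute-0 screening, state them in the information sheet, and submit the change as an amendment to the ethics approval. If the screening form and information sheet already cover both, only the two list items are needed.

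The cost is two lines in the protocol, a few questions at an existing step, the amendment paperwork and a slightly smaller recruitment pool. Sample size, randomisation, the rest of the session and the analysis stay as they are. Self-report will not detect an unsuspected pregnancy, so the gain is limited to conditions the participant knows of or suspects.

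### Randomisation is stratified by sex but no planned ANOVA contains sex, so drink-effect standard errors will be too large to the extent that sex is prognostic

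*Protocol*

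**What the plan says.** Three parts of the protocol deal with sex at the design stage.

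- Randomisation: "Equal numbers of participants per group will be maintained and groups will be stratified by sex".
- Participants and Recruitment: "Male and female weekly alcohol drinkers (n = 192; 50% male) will be recruited".
- Sample size determination: the calculation gives 190, and recruitment is set at 192 to keep the sexes equal within drink groups. 190 is not divisible by four. 192 is, giving 96 per arm and 48 of each sex per arm.

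The parts that describe the analysis do not mention sex.

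- Study Design describes a study "which comprises one between-subjects factor of drink (0.4 g/kg alcohol, placebo").
- Statistical Plan, emotion tasks: "Emotional task data from both tasks will also be analysed using ANOVAs with alcohol consumption as a between-subjects factor". For the 6AFC it adds: "The 6AFC task will have an additional within-subjects factor of emotion".
- Statistical Plan, questionnaires: "mixed model ANOVAs with alcohol consumption (alcohol vs. placebo) as a between-subjects factors and time as a within subjects factor".

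The protocol says nothing about how strongly sex relates to false alarms, accuracy, the 2AFC threshold or the questionnaire scores.

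**The concern.** When allocation is balanced on a factor, that factor's variation no longer contributes to the difference between arms. An analysis that leaves the factor out still counts the variation as error. The reported standard error then exceeds the true sampling variability of the estimate, and the test runs below its nominal 5% level.

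At stake is the accuracy of the reported precision for the comparisons that test H1 and H2, and a little power. The design treats sex as worth balancing and sets the final sample size accordingly, while the models as described do not follow the design.

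**Working it through.** **Inputs.** From Sample size determination: "d = 0.41 for the comparison between alcohol (M = 4.8, SD = 4.2) and placebo (M = 3.2, SD = 3.6) on angry false alarms", and "we require a sample size of 190 in order to achieve 80% power at an alpha level of 5"%. Allocation is 96 per arm with 48 of each sex. R2, the share of within-arm outcome variance explained by sex, is not in the protocol and is assumed over a range.

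**Step 1: reproduce the plan's figure.** Pooled SD = sqrt((4.2² + 3.6²)/2) = sqrt(15.30) = 3.91, and d = 1.6/3.91 = 0.409, which agrees with 0.41. A two-sided 5% two-sample t test with 80% power needs 95 per arm, 190 in all. The normal approximation gives 188, and a one-sided test gives 148. The stated 190 is therefore a two-sided calculation that takes no credit for sex. Power at 96 per arm is 80.7%.

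**Step 2: true and reported variance.** Set the within-arm SD to 1. With equal numbers of each sex in each arm, the sex effect cancels from the difference in means.

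- True variance of the drink difference: 2(1 - R2)/96.
- Variance estimated by a model without sex: about 2/96.
- Ratio of reported to true standard error: 1/sqrt(1 - R2).

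For R2 = 1%, 5% and 10% the ratio is 1/sqrt(0.99) = 1.005, 1/sqrt(0.95) = 1.026 and 1/sqrt(0.90) = 1.054.

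**Step 3: type I error without sex.** This is approximately 2[1 - Φ(1.96/sqrt(1 - R2))]. At R2 = 5%, 1.96 × 1.026 = 2.011, which gives 0.044.

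**Step 4: power, d = 0.41, N = 192.** With sex in the model, power comes from the noncentral t distribution with 189 degrees of freedom and noncentrality 0.41/sqrt(2(1 - R2)/96). Without sex, the estimate has the true variance from step 2 but is judged against the inflated standard error (190 degrees of freedom). That power was obtained by integrating over the distribution of the estimated error variance.

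| Assumed R2 | Male-female difference, 2·sqrt(R2), in SDs | SE overstated by | Type I error without sex | Power without sex | Power with sex |
|---|---|---|---|---|---|
| 0% | 0 | 0% | 0.050 | 80.7% | 80.7% |
| 1% | 0.20 | 0.5% | 0.049 | 80.8% | 81.1% |
| 5% | 0.45 | 2.6% | 0.044 | 81.3% | 82.6% |
| 10% | 0.63 | 5.4% | 0.039 | 81.9% | 84.6% |
| 20% | 0.89 | 11.8% | 0.028 | 83.3% | 88.5% |

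A simulation with 40,000 runs per setting and 48 per sex per arm gave power within about 0.2 percentage points of these values. Its type I error was within about 0.002 of the table without sex and between 0.048 and 0.050 with sex. All of this assumes normally distributed outcomes and an additive sex effect.

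**Step 5: which tests are affected.** The drink main effects, the drink contrast within a single emotion (the comparison used for the sample size) and the 2AFC threshold all compare levels between people, so steps 2 to 4 apply. The drink-by-time and drink-by-emotion tests compare differences within people. A sex effect that is constant over time or emotion subtracts out, and a sex main effect leaves those tests unchanged. Only a sex-by-time or sex-by-emotion effect would matter there.

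**The case against.** The strongest reply has four parts.

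1. **The effect is conditional.** A reader might infer that the standard errors are certainly too large. The protocol does not support that, because it gives no evidence that sex predicts any outcome. At R2 = 0 nothing is lost. R2 = 5% already requires a male-female difference of 0.45 SD, larger than the drink effect of 0.41 used for planning. This part stands.
2. **Stratification still works.** A reader might infer that its benefit is thrown away. It is not. With balanced cells the estimated drink difference is the same with or without sex in the model, it remains protected from chance sex imbalance, and its true variance is reduced under either model. Only the reported precision suffers, and in the conservative direction. This part stands.
3. **The gain is easily overstated.** Measuring it from a fixed 80.7% is wrong, because that figure belongs to R2 = 0 and power without sex also rises with R2 under exact balance. The gain is about 1.3 points at R2 = 5% (not 1.9) and 2.7 points at 10% (not 3.9). This part stands.
4. **A statistical analysis plan may add sex.** None is shown, covariates are often settled there, and the Statistical Plan calls drink a between-subjects factor without saying it is the only one. This stands only in part. Study Design counts one such factor, and the Statistical Plan names the factors for each family of analyses without sex. The mismatch is therefore in the protocol's own text. It could be argued that Study Design means only the manipulated factor, but then the protocol should say how the stratification factor is handled.

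**Conclusion.** The point holds as a modest, conditional mismatch between randomisation and analysis. To the extent that sex is prognostic, the planned models overstate the standard error by 1/sqrt(1 - R2) for the drink main effects, the per-emotion contrasts behind H1 and H2, and the 2AFC threshold. Over an assumed R2 of 1% to 10%, that is 0.5% to 5.4% in the standard error, a true type I error of about 0.049 down to 0.039, and 0.3 to 2.7 percentage points of power forgone.

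A reader might go further and infer that the trial is underpowered, its estimate biased, or every planned test affected. None of these follows. The 190 was derived without credit for sex, power at 192 is at least 80.7% throughout the range examined, the drink estimate is unbiased, and a constant sex effect does not touch the drink-by-emotion or drink-by-time tests. The size of the effect rests entirely on the assumed R2. The direction does not depend on its value, provided that it is above zero.

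**What to change.** In the Statistical Plan, add sex as a between-subjects main effect to the 6AFC ANOVAs, including the per-emotion drink contrasts for H1 and H2, and to the 2AFC ANOVA. Add it to the questionnaire ANOVAs for the sake of the drink main effect, and note that it will not alter the drink-by-time test. Amend Study Design so that drink is described as the experimental between-subjects factor and sex as the stratification factor included in the models.

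The cost is one degree of freedom (190 to 189) and a few words of text. Sex has to be known for every participant before stratified allocation, so no new data are needed, and the sample size does not change. If sex turns out to be unrelated to the outcome, power is 80.7% either way. Specifying the term now also removes a discretionary choice about adjustment later, which is useful in a replication study.
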